6.4 Summary of known and potential risks and benefits

Pilocarpine is a cholinergic parasympathomimetic agent exerting a broad spectrum of pharmacologic effects with predominant muscarinic action.[30]

- In systemic use pilocarpine, in appropriate dosage, can increase secretion by the exocrine glands. The sweat, salivary, lacrimal, gastric, pancreatic, and intestinal glands and the mucous cells of the respiratory tract may be stimulated. Dose-related smooth muscle stimulation of the intestinal tract may cause increased tone, increased motility, spasm, and tenesmus. Bronchial smooth muscle tone may increase. The tone and motility of urinary tract, gallbladder, and biliary duct smooth muscle may be enhanced. Pilocarpine may have paradoxical effects on the cardiovascular system. The expected effect of a muscarinic agonist is vasodepression, but administration of pilocarpine may produce hypertension after a brief episode of hypotension. Bradycardia and tachycardia have both been reported with use of pilocarpine.

- In use as eye drops: systemic reactions rarely occur when treating chronic simple glaucoma at normal doses. However, in the treatment of acute closed-angle glaucoma the possibility of systemic reactions must be considered because of the higher doses given. Caution is particularly advised in patients with acute heart failure, bronchial asthma, peptic ulceration, hypertension, urinary tract obstruction, Parkinson's disease and corneal abrasions.[31]

Contraindications:

Pilocarpine HCl Tablets are contraindicated in patients with uncontrolled asthma, known hypersensitivity to pilocarpine, and when miosis is undesirable, e.g., in acute iritis and in narrow-angle (angle closure) glaucoma.

Pilocarpine eye drops are contraindicated in conditions where pupillary constriction is undesirable e.g. acute iritis, anterior uveitis and some forms of secondary glaucoma.

Pilocarpine eye drops are also contraindicated in case of hypersensitivity to the active substance or to any of the excipients thereof.

6.5 Description and justification of route of administration and dosage

Polypharmacy is common among elderly patients; patients may even object against more “pills”. In a crossover study in advanced cancer patients, pilocarpine tablets was found to be more effective than artificial saliva, however 50% of patients preferred the saliva. The commonest reason for preferring the artificial saliva was the fact that it was a spray, rather than a tablet.[32]

Patients don't experience local application as “pills”, which makes pilocarpine drops better acceptable. Moreover, local oral administration of pilocarpine (drops, lozenges and mouthwashes) are reported to have none [24, 25] or minor local side effects.[26]

6.6 Dosages, dosage modifications and method of administration

The two doses pilocarpine nitrate (3 x 2.0 mg = 3 x 2 drops or 3 x 5.0 mg = 3 x 5 drops) will be stable over the first 14 days of the study. Day 15 through day 21 patients will not receive medication. Drops will be administered left and right outside the molars and behind the front teeth under.

6.7 Preparation and labeling of Investigational Medicinal Product

The pilocarpine nitrate drops are commercially available (Bausch & Lomb), registered for treatment of open-angle glaucoma and narrow-angle glaucoma and to antagonize mydriasis.

6.8 Drug accountability

Drug accountability will be done at the Pharmacy.

7. NON-investigational products

NA

8. METHODS

8.1 Study parameters/endpoints

8.1.1 Main study parameter/endpoint

- change in xerostomia score (NRS)
- change in oral health-related quality of life (GOHAI-NL)

8.1.2 Secondary study parameters/endpoints

- Adverse effects
- Other symptoms
- Global perceived effect

8.1.3 Other study parameters (if applicable)

- whole resting salivary flow

8.2 Randomisation, blinding and treatment allocation

Randomisation will be performed by a sealed envelope system.

In this participating clinicians are given treatment allocations randomly drawn from one of 24 sealed opaque envelopes that include 12 allocations to the low dose, and 12 to the high dose group to ensure perfect balance. Once a patient has consented to enter the study an envelope is opened and the patient is then offered the allocated treatment regimen.

8.3 Study procedures

The study will be performed at the outpatient clinic internal medicine/elderly care of the Maastricht University Medical Centre+. Potentially eligible patients will be identified on the outpatient clinic by answering the question if they have suffered from a dry mouth in the last three months. If the answer to this question is yes they will be invited to participate when meeting the inclusion criteria.

Each patient that participates in this study will receive a restaurant coupon and their travel expenses will be covered.

Randomisation will occur through a sealed envelope system. Once a patient has consented to the trial, a sealed opaque envelope is opened and the patient will receive the allocated treatment regime. This sealed opaque envelope will also contain a two digit number wherein the patient will be identified from this point forward in the database. The sealed opaque envelopes with all its content will be arranged by the researcher before start of the study.

Measures will be performed on day 0, 7, 14 and 21. Questionnaires on day 0, 7, 14 and 21, whole resting salivary flow on day 0 and 14, blood pressure will be measured on day 0 before and 1 hour after pilocarpine administration and on day 14.

	Day 0	Day 7	Day 14	Day 21
Hospital visit	X		X	
Patient characteristics	X			
Xerostomia NRS / GOHAI-NL	X	X	X	X
USD	X	X	X	X
EQ5D	X	X	X	X
GPE	X	X	X	X
Side effects	X	X	X	X
RR	X		X	
Whole resting saliva	X		X	

After inclusion the patient will visit the outpatient clinic twice on day 0 and day 14. On the first visit (day 0) after inclusion a questionnaire consisting of 45 questions, will be filled in, this will take 20 minutes. Also patient characteristics, including use of medication, will be accessed. Blood pressure and whole resting saliva will be measured. The blood pressure will be measured in sitting position using the Dinamap technology V100 care scape from general electric. The whole resting saliva will be measured by the doctor/research nurse. The patient will have to sit straight in a chair and will be asked to swallow the saliva that is currently in their mouth, in the next five minutes the patient will be asked to accumulate all the saliva that is spontaneously produced in their mouth. This whole resting saliva will be collected in a previously weighted cup and the result of each patient will be compared. The cups and the whole resting saliva will be measured with the SARTORIUS AC210p scale.

On day 14 all of these procedures but one (assessment of patient characteristic) will be repeated. On day 7 and day 21 the patient will receive a phone call wherein the questionnaires will be taken by the doctor/research nurse. At the end of the study patients will be offered to continue the pilocarpine drops as off-label use. The reimbursement status for this indication is uncertain.

Table 1: Description of study procedures

	Procedure	Parameter	Description
Measurements	Whole resting saliva	Amount of saliva collected in 5 minutes	This procedure will be done twice during the study
	Blood pressure	mmHg	The sitting blood pressure will be measured using the Dinamap technology V100 care scape from general electric.
Questionnaires	0-10 Numeric Rating Scale (NRS)	Xerostomia	The NRS is used to quantify the level of severity of xerostomia using a 0-10 cm NRS ranging from 0 = no dry mouth to 10 = worst possible dry mouth.[28]
	Geriatric Oral Health Assessment Index (GOHAI-NL)	Xerostomia	Oral health-related quality of life (OHRQoL) of adults, in particular older people is measured 4 times during this study by the doctor/research nurse . It comprises of 12 items that measure three dimensions of OHRQoL: physical function items, psychosocial function and pain/discomfort. [33]
	Utrecht symptom Diary (USD)	concurrent symptoms	The USD asks patients to self-asses eleven symptoms and their wellbeing on a daily basis, by using a numerical rating scale ranging from 0 to 10. Patients can also indicate which symptom is a priority for them.[34, 35]
	EuroQoL 5D (EQ5D)	generic Health-Related Quality of Life (HRQoL)	Health-related quality of life is measured 4 times during this study by the doctor/research nurse, using five dimensions: mobility, self-care, usual activities, pain/discomfort and anxiety/depression.[36]

	Global Perceived Effect (GPE 7-point scale)	Global Perceived Effect (GPE)	The GPE scale asks the patient to rate, on a numerical scale, how much their condition has improved or deteriorated since some predefined time point.[37]
	4-point Likert scale	Side effects	Patients are asked if they experienced flu-like symptoms, sweating, headache, urinary frequency, diarrhoea, nausea, vomiting, palpitations, dizziness, rhinitis, or other symptoms, while on the treatment.

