11.2 Recruitment and consent

Patients who fulfill the inclusion criteria, will be informed about the study by their treating physician or physician assistant during a regular outpatient clinic visit. The treating physician or physician assistant will hand out the patient information leaflet and introduce the patient to the researcher.

The patient will have a minimum of 7 days period to decide if he or she wants to participate in the study. If a patient decides to participate, the researcher will plan a new appointment for the patient where additional questions can be answered and the informed consent can be signed. This day will be considered day 0, and the start of the study for this patient.

Inclusion will take place on Tuesdays and Wednesdays in the outpatient clinic of internal medicine. On these days there are the largest amount of patients at the outpatient clinic. A total of 6 patients per doctor is expected to be seen. This means that on a Tuesday about 18 patients will be seen and on a Wednesday 12 patients.

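### The protocol separates envelope preparation from enrolment nowhere, and ties no envelope to a patient before it is opened

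*Protocol*

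**What the plan says.** Four parts of the protocol bear on this.

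- **Preparation (section 8.3).** "The sealed opaque envelopes with all its content will be arranged by the researcher before start of the study". The same paragraph puts the identifier inside: "This sealed opaque envelope will also contain a two digit number wherein the patient will be identified from this point forward in the database".
- **Draw (section 8.2).** Participating clinicians are "given treatment allocations randomly drawn from one of 24 sealed opaque envelopes", 12 for each dose, in order "to ensure perfect balance". On timing: "Once a patient has consented to enter the study an envelope is opened".
- **Contact and consent (section 11.2).** The treating physician or physician assistant "will hand out the patient information leaflet and introduce the patient to the researcher". After the time for reflection, "the researcher will plan a new appointment for the patient where additional questions can be answered and the informed consent can be signed". That day is day 0.
- **Blinding (section 3).** The trial is open-label.

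The protocol describes no independent preparer or holder of the envelopes, no number on the outside, no order of opening, no log of opened envelopes, and no step that links a patient to an envelope before the seal is broken.

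**The concern.** Concealment of allocation needs two things. Whoever decides that a patient enters should not know, or be able to influence, what comes next. The assignment should also be irrevocable from the moment it is disclosed.

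The protocol secures neither fully. The role that fills the envelopes carries the same name as the role that meets the patient and arranges the consent visit. And because an envelope is taken from a pool and shows its number only once opened, nothing binds it to the patient in advance. Someone who opens an envelope and finds the allocation unsuitable for that patient could put it aside and take another.

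There is no placebo group, so low against high dose is the only randomised contrast. The NRS and the side-effect scores are patient-reported under open treatment. If patients thought likely to tolerate the drug poorly went preferentially to one dose, the comparison between doses would be biased. The composition of each arm would change too, and with it the per-dose results that are to inform a later trial (sections 2 and 4.4).

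**Working it through.** **1. The plan's own count.** Section 8.2 has 12 + 12 = 24 envelopes, which agrees with the planned 24 patients, 12 per group, in section 4.4. There is no power calculation to reproduce.

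**2. Who does what.**

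| Step | Role named | Section |
|---|---|---|
| Fills and seals the envelopes | the researcher | 8.3 |
| Identifies and informs patients | treating physician or physician assistant | 11.2 |
| Is introduced to the patient, plans the day-0 visit | the researcher | 11.2 |
| Is given the drawn allocation | participating clinicians | 8.2 |
| Accounts for the drug | pharmacy | 6.8 |

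The first and third rows carry the same label, and no text keeps them apart. The pharmacy is given no part in enrolment.

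**3. When an envelope becomes tied to a patient.** Sections 8.2 and 8.3 give the sequence consent, draw, open, read number and dose. The link arises at the last step. Suppose an opened envelope is set aside, a second one is drawn for this patient, and the first is used for the next patient. At the first patient, the second draw shows the other dose with probability 12/23 = 0.52. At the end all 24 numbers have been used and the totals are still 12 and 12. Because the pool is drawn at random, the numbers need not follow the order of entry, so comparing numbers with entry dates would not show a departure.

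**4. Leverage.** One patient is 1/12 = 8.3% of an arm, and two are 2/12 = 16.7%. If two patients whose NRS change differs by *d* points exchange arms, each arm mean moves by *d*/12 in opposite directions, and the difference between arms moves by 2*d*/12 = *d*/6. For each point of *d* that is 0.08 per arm and 0.17 between arms. The protocol gives no figure for *d* or for how often this might happen, so no expected bias can be computed.

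**The case against.** Several counter-arguments have force.

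- **The safeguards are real.** The envelopes are sealed and opaque and are opened only after consent. A random draw is itself a barrier: filling 24 envelopes does not tell the preparer which one comes next. A reader might infer that the preparer can foresee the allocations. That would require marked envelopes or a known order, and the protocol describes neither.
- **The roles may be held by different people.** The researcher of 8.3 need not be the researcher of 11.2; section 12.1 speaks of researchers in the plural. The finding is that no separation is stated, not that one person does both.
- **The outside may carry a number.** The protocol places a number inside and mentions none outside. That the envelopes are unnumbered is an inference.
- **A swap might be noticed.** A broken seal, the code list of section 12.1 or a visit under section 12.2 could reveal one. It would go too far to say that no record would show it. What can be said is that the protocol describes no reconciliation of envelopes.
- **The fixed 12:12 total is not the problem.** A reader might add that in an open trial a running tally predicts later allocations. Always guessing the arm with more envelopes left gives 12 + (4^12/C(24,12) − 1)/2 = 12 + (16,777,216/2,704,156 − 1)/2 = 14.60 correct of 24 (60.8%), against 12 under simple randomisation. But blocks of 4 would give 17.0 and blocks of 6 would give 16.4, so one pool of 24 is less predictable than those. The fix below leaves the figure unchanged, so it is no argument for the fix.
- **The between-dose test is exploratory.** Section 10 puts the emphasis on each group separately. This limits the consequence but does not remove it, since selection also alters who is in each group.
- **Numbering and logs may sit in a trial manual.** They may, but sections 8.2 and 8.3 themselves set a draw from a pool and name the preparer, and that stated procedure is what needs to change.

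**Conclusion.** The point holds as a moderate weakness in allocation concealment. The protocol assigns preparation of the envelopes to a role with the same name as the one that meets patients and plans the consent visit, without separating them. It also prescribes a draw that commits no envelope to a patient before opening. The second part is the firmer one, because it follows from the stated sequence whoever holds the roles.

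The size is a matter of leverage: 8.3% of an arm for each patient, and *d*/6 NRS points on the dose contrast for each exchanged pair. How often it would occur cannot be derived from the document. The conclusion assumes that no separate procedure already prescribes independent preparation and ordered opening. It does not rest on foresight by the preparer, on the 12:12 tally or on any suggestion of misconduct. It deserves correction before enrolment, but does not by itself invalidate the study.

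**What to change.** Amend sections 8.2 and 8.3 together:

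1. Someone with no part in enrolment generates the allocation list and prepares the envelopes. The pharmacy, already responsible for drug accountability, is a natural choice.
2. The envelopes are numbered 01 to 24 on the outside, and that number serves as the subject code.
3. After consent, the patient's identification and the date are written on the next envelope, and only then is it opened. Envelopes are used strictly in order, and the wording about a random draw is replaced accordingly.
4. The monitor reconciles used and unused envelopes with the list at the visits already planned in section 12.2.

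Items 1 and 3 belong together: a fixed order without an independent preparer would remove the protection that the random draw now gives. Marked envelopes identify patients, so they should be kept as securely as the code key in section 12.1.

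The cost is one small preparation task for the pharmacy and a few lines of protocol text. Sample size, visits and analysis do not change.

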Current symptomatic treatment options include local treatment with artificial saliva/mouthwashes or systemic or local administration of pilocarpine. The former has mainly been researched in advanced cancer patients[12, 13] and was not better than chewing gum.[14] The latter are the current mainstay treatment of patients in the palliative phase of their illness.[12] Pilocarpine is a parasympathomimetic drug that increases saliva production by activating muscarinic receptors.[12] Pilocarpine tablets (systemic treatment) are more effective than placebo in radiation-induced xerostomia,[15-18] Sjögrens disease, [19] tramadol induced oral dryness[20] and improved salivation in patients taking xerogenic medications.[21] However, systemic administration of pilocarpine has frequent side-effects such as sweating (20 -50%), flushing, rhinitis (12%), headaches (12%), increased frequency of urination (11-34%), flu-like symptoms (8%), asthenia (7%)[21-23] and, mainly in elderly patients, dizziness (17%) leading to dropout rates between 6% and 15% in clinical studies.[16] Local oral administration of pilocarpine (drops, lozenges and mouthwashes) are reported to have none [24, 25] or minor local side effects (irritation of mouth and tongue).[26] In addition, a 5 mg pilocarpine lozenge produced better clinical results than a 5 mg pilocarpine tablet in 33 head-and-neck cancer

patients.[27], Furthermore, pilocarpine eye drops 2% relieved xerostomia immediately in 19 patients with opioid-induced complaints of dry mouth.[25] However, inconclusive results have been reported about the effectiveness of these local formulations in other studies.[24, 28].

Literature is scarce on the effectiveness of pilocarpine in elderly patients with xerostomia.

Pilocarpine mouthwash relieved dry mouth in 19 elderly patients[26], whereas a systematic review evaluating the effectiveness of systemic pilocarpine in 242 elderly patients with xerostomia due to medication or unknown causes showed inconclusive results.[1] As our population is ageing and poly-pharmacy is common among elderly, more patients will be poly-medicated in the future. Hence, xerostomia will be a major problem and thus more research on this topic is necessary.

This study intends to deliver the “proof-of-concept” that locally administered pilocarpine drops are effective in reducing xerostomia complaints in a population of elderly (aged ≥ 70 years) with xerostomia at the expense of a minimum of side effects.

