3. STUDY DESIGN

DESIGN:

Open-label randomised controlled pilot study

PARTICIPANTS

The study will be performed at the outpatient clinic internal medicine/elderly care of the Maastricht University Medical Centre+.

INTERVENTION:

The intervention concerns the treatment of xerostomia in 2 treatment groups:

1. low dose pilocarpine = 3 x 2.0 mg = 3 x 2 drops of pilocarpine 20.0 mg/ml (2%) per day
2. high dose pilocarpine = 3 x 5.0 mg = 3 x 5 drops of pilocarpine 20.0 mg/ml (2%) per day

The study lasts 21 days of which the first 14 days with medication and the last 7 days without medication to measure a possible “switch-on” effect.

MEASUREMENTS

Xerostomia	Numeric Rating Scale (NRS) Geriatric Oral Health Assessment Index (GOHAI-NL)
Concurrent symptoms	Utrecht symptom Diary (USD)
Generic Health-Related Quality of Life (HRQoL)	EuroQoL 5D (EQ5D)
Global Perceived Effect (GPE)	GPE 7-point scale
Side effects	4-point Likert scale (flu-like symptoms, sweating, headache, urinary frequency, diarrhoea, nausea, vomiting, palpitations, dizziness, rhinitis, other)
Whole resting saliva	Total amount of unstimulated saliva measured in 5minutes

Patient characteristics that are collected at inclusion include gender, age, primary diagnosis, co-morbidity, medication and relevant history.

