6.3 Summary of findings from clinical studies

Pilocarpine tablets are registered for dry mouth in Sjögrens disease and post radiation therapy.

Pilocarpine drops are registered for treatment of open-angle glaucoma and narrow-angle glaucoma and to antagonize mydriasis.

Pilocarpine tablets (systemic treatment) has proven to be effective in radiation-induced xerostomia,[15-18] Sjögrens disease, [19] tramadol induced oral dryness[20] and in patients taking xerogenic medications.[21] However, systemic administration of pilocarpine has frequent side-effects.

Off-label local oral administration of pilocarpine (drops, lozenges and mouthwashes) are reported to have none [24, 25] or minor local side effects (irritation of mouth and tongue).[26] In addition, a 5 mg pilocarpine lozenge produced better clinical results than a 5 mg pilocarpine tablet in 33 head-and-neck cancer patients.[27], Furthermore, pilocarpine eye drops 2% relieved xerostomia immediately in 19 patients with opioid-induced complaints of dry mouth.[25] However, inconclusive results have been reported about the effectiveness of these local formulations in other studies.[24, 28].

Dosing:

Post-radiation studies reveal an optimum oral dose of 5 mg 3 dd/day. Higher doses result in higher saliva flow but at the expense of more unacceptable adverse effects. Effect and side effects increase with increasing dosages.[15, 16] A trial with 2,5 mg 3dd/day showed an increase in salivary flow but not a subjective improvement.[18] Possibly this low dose is insufficient in damaged salivary glands. In this pilot study we will compare two doses (5 mg 3 dd/day and 2mg 3dd/day) in intact glands.

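### The side-effect checklist does not name irritation of mouth and tongue, the only side effect the protocol names for local oral pilocarpine; adding it is a cheap improvement

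*Protocol*

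**What the plan says.** The checklist appears twice in the protocol with the same content. Section 3 gives a 4-point Likert scale covering "flu-like symptoms, sweating, headache, urinary frequency, diarrhoea, nausea, vomiting, palpitations, dizziness, rhinitis, other". Table 1 in section 8.3 says "Patients are asked if they experienced flu-like symptoms, sweating, headache, urinary frequency, diarrhoea, nausea, vomiting, palpitations, dizziness, rhinitis, or other symptoms", and the sentence ends by tying the question to the time on treatment. The schedule in section 8.3 places this form on days 0, 7, 14 and 21.

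On what to expect from the drug, section 1 separates two routes. For tablets, "systemic administration of pilocarpine has frequent side-effects such as sweating", followed by further systemic effects. For drops, lozenges and mouthwashes it reports either no side effects or "minor local side effects (irritation of mouth and tongue"; section 6.3 repeats this. Section 6.5 again mentions minor local effects and names no others.

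On the route used here, section 6.6 states "Drops will be administered left and right outside the molars and behind the front teeth under". Section 8.1.2 lists "Adverse effects" as a secondary endpoint, and the objective in section 2 couples effectiveness with few adverse events.

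**The concern.** The trial puts drops onto the oral mucosa, and part of the case for that route is its mild side-effect profile. The one side effect the protocol attaches to the route is the one the form does not ask about by name. Patients are asked outright about sweating or headache, but must raise a sore mouth or tongue themselves when asked about anything else.

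The number of irritation reports under the open item then depends on how each patient, and each doctor or nurse taking the questionnaire, uses that item. A low count could mean that few patients had irritation or that few mentioned it. This matters most for the comparison of doses, because the arms differ in the amount applied locally (2 against 5 drops, three times a day).

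A second matter concerns the baseline. Section 1 lists pain and burning among the consequences of dry mouth itself, so a mouth complaint on day 7 or 14 is hard to read without a pre-treatment answer. The form is scheduled for day 0, but the protocol does not say whether it is completed before or after the dose given that day.

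**Working it through.** No figure of the protocol needs reproducing here; the check is mainly a comparison of texts.

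1. **Items on the form.** Sections 3 and 8.3 list the same ten named effects plus an open item. Neither list has a mouth or tongue item.

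2. **Where the items come from.** Six of the ten (dizziness, flu-like symptoms, headache, rhinitis, sweating, urinary frequency) are in section 1's list for systemic pilocarpine. The other four are three gastrointestinal complaints and palpitations. None is a local oral effect.

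3. **Local effect named by the protocol.** There is one, irritation of mouth and tongue (sections 1 and 6.3). It is not a named item.

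4. **Other routes of capture.**
   - The open item: it is asked on all four days, but its content is whatever the patient brings up.
   - Section 9.2.1: all spontaneously reported or observed adverse events are recorded. This depends on mention or observation.
   - GOHAI-NL: its 12 items include a pain/discomfort dimension, scored on all four days. It is a main endpoint, so irritation captured there would count as poorer oral quality of life, not as a side effect.
   - Utrecht Symptom Diary: its eleven symptoms are not listed in the protocol, so an oral item can be neither assumed nor excluded.

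   As described, none of these is a defined side-effect variable for irritation graded in every patient.

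5. **Use at analysis.** Section 10 plans counts and proportions for categorical secondary measures, with exploratory Fisher's exact tests between arms. A named item fits this directly. Free mentions would first have to be classified, and silence would have to be read as absence.

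6. **Timing and recall.** Section 8.3 says "blood pressure will be measured on day 0 before and 1 hour after pilocarpine administration", so a dose is given on day 0, while the order of the side-effect form and that dose is not stated. A question about the time on treatment does not suit a pre-dose form. It is also unclear on day 21, since days 15 to 21 are off drug (section 6.6).

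7. **Illustration only.** The protocol gives neither an irritation rate p nor the share s of affected patients whose irritation is recorded; both are assumed here. The chance of at least one record in an arm of 12 is 1 − (1 − p·s)^12. With p = 20%:
   - s = 1: 1 − 0.80^12 = 93%
   - s = 0.5: 1 − 0.90^12 = 72%
   - s = 0.25: 1 − 0.95^12 = 46%

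   For p from 10% to 30%, the range is 72% to 99% at s = 1 and 26% to 61% at s = 0.25. These figures show how incomplete capture would act in a small arm. They do not estimate what will happen.

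8. **Effect of the change on the form.** Named items: 10 + 1 = 11, plus the open item. Question count: 45 + 1 = 46 if the new item counts as one question.

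**The case against.** The case for leaving the form alone is a fair one. The open item is itself prompted, and on days 7 and 21 a doctor or research nurse takes the questionnaires by phone. Spontaneous and observed adverse events are recorded as well, and the GOHAI-NL gives an oral discomfort measure with a baseline and three follow-ups. A mainly systemic list also fits the rationale: the drops are meant to avoid the systemic effects of tablets, so asking whether those effects still occur is the natural safety question. Section 8.7 expects no or only minor side effects. Flushing and asthenia, also named in section 1 for systemic use, are likewise not on the list.

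Most of this stands and limits the point. A reader might infer that the protocol contradicts itself, or that irritation would go unrecorded and be lost to any analysis. The documents support neither reading: there are several routes of capture, and the GOHAI-NL data would remain available. That capture under the open item is less uniform than under a named one is a reasonable expectation, not something the protocol shows.

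What does not stand is that these routes replace a named item. The open item and adverse-event recording do not ask every patient about irritation specifically, and the GOHAI-NL does not classify it as a side effect. Flushing and asthenia do not weaken the point, since they are not tied to the local route.

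**Conclusion.** The point holds as a low-cost improvement to data collection. The form asks by name about ten mainly systemic effects and leaves to the open item the only effect the protocol names for the route under test. The plan therefore has no defined, graded irritation variable to compare between 2 and 5 drops.

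The size of the loss cannot be derived from the protocol. The consequence is limited to one secondary endpoint, reported mainly descriptively, in a pilot of 24 patients (12 per group), for an effect described as minor. No main endpoint, sample size or planned test changes.

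The conclusion assumes that irritation is not already a separate item in the Utrecht Symptom Diary, which the protocol does not settle. A reader might also infer that a named item would show what the drug causes. It would not: both arms receive pilocarpine and the study is open-label, so attribution would remain unproven.

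**What to change.** - In section 3 and in Table 1 of section 8.3, add irritation of mouth or tongue as a named item on the 4-point scale, asked on days 0, 7, 14 and 21. Leave burning out of the wording: section 1 gives it as a consequence of dry mouth, so one item covering both would mix treatment benefit with harm.
- State that the day-0 form is completed before the first dose and serves as the baseline.
- Replace the reference to being on treatment with a recall period that fits each time point, including day 21, when patients are off the drug.
- Update the stated number of questions in the Summary and section 8.3 (46 if the item counts as one question).

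The cost is one more question at four time points and a few words on timing and recall. The form becomes slightly longer, and more local effects may be reported because they are asked about. The design, sample size and analysis methods stay as they are.
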